## 4.2 Exclusion Criteria

### *Both Phases*

1. (AML cohort closed) AML M3 by FAB classification (APL)
2. Known, current central nervous system disease involvement or untreated brain metastases
3. Investigational agent or any anticancer drug within 14 days prior to planned start of treatment (with the exception of hydroxyurea in subjects with MPN, MPN/MDS, ALL or AML; see [Section 6.8.2](#))
4. Allogeneic transplant within 30 days prior to the planned start of treatment or subjects with active graft-vs-host disease with the exception of Grade 1 skin involvement (see [Appendix C](#))
5. Prior anti-CD47 therapy, with the exception of prior TTI-621 therapy delivered intratumorally only
6. Major surgery within 28 days prior to planned start of treatment

7. Use of irreversible antiplatelet/anticoagulant agents within 7 days prior to planned start of treatment (except subjects with thrombocytosis where low dose aspirin is being used to reduce the risk of thrombosis); use of low dose aspirin ( $\leq 81$  mg/day) and selected, reversible anticoagulants are permitted (low molecular weight heparin, heparin, warfarin and dabigatran)
8. History of hemolytic anemia or bleeding diathesis
9. Uncontrolled infection requiring systemic antibiotics/antivirals/antifungals
10. Chronic use of systemic corticosteroids of more than 20 mg per day of prednisone or equivalent; enrollment of post-transplant subjects who are on corticosteroids for graft-vs-host disease prophylaxis requires approval of the Medical Monitor. CTCL patients who are on a stable dose of medium or low potency topical corticosteroids for at least 4 weeks prior to study entry may continue its use on study at the same dose.
11. Known hypersensitivity to any component of study drug
12. Positive serum pregnancy test in females of child-bearing potential or current breastfeeding
13. Significant cardiovascular disease such as symptomatic congestive heart failure (New York Heart Association Class III or IV), symptomatic coronary artery disease, myocardial infarction within the last 6 months, unstable arrhythmia requiring treatment, unstable angina, or prolonged QTc interval  $> 480$  milliseconds (Grade 2 or higher) (QTc interval calculation at the discretion of the Investigator)
14. Active hepatitis B or C or a history of HIV infection
15. Other significant medical condition unrelated to the primary malignancy that would compromise subject's safety or ability to comply with protocol requirements
16. Inability for the subject to complete protocol requirements, such as geographic considerations, psychiatric disorders, or other compliance concerns
17. Prior Grade 4 rituximab infusion-related reaction (rituximab combination arm only)
18. Active autoimmune disease or history of autoimmune disease that might recur (nivolumab combination arm only); subjects with vitiligo or type I diabetes mellitus or residual hypothyroidism due to autoimmune thyroiditis only requiring hormone replacement are permitted to enroll

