### **6.8.2 Allowed Concomitant Treatments**

The Investigator is permitted to use standard supportive care for symptom control or drug-related toxicity; this might include analgesics, antiemetics, electrolyte replacement, topical steroids, hydration, and/or blood product transfusions. Other prescribed medications for non-neoplastic conditions are allowed, as well as vitamins and nutritional supplements. Chronic use of steroid above a daily equivalent dose of 20 mg prednisone is not permitted on study with the exception of CTCL patients who had been on a stable dose of medium or low-potency topical steroid for 4 weeks before the first dosing of the study drug. These patients can continue to use the same dose of topical steroid for symptom control on study.

Use of selected reversible anticoagulants (low molecular weight heparin, heparin, warfarin or dabigatran) for prevention or treatment of thrombosis is permitted per the

2017 National Comprehensive Cancer Network (NCCN) guidelines, “Cancer-Associated Venous Thromboembolic Disease”, with dose adjustments for thrombocytopenia per local institutional guidelines, with maintenance of platelet count  $>50 \times 10^9/L$  or per local institutional standard. Use of low dose aspirin ( $\leq 81 \text{ mg day}$ ) is permitted for control of malignant thrombocytosis.

Myeloid growth factors are permitted for rescue from treatment-emergent Grade 3 or 4 neutropenia. Likewise, erythropoiesis-stimulating or megakaryopoiesis-stimulating agents may be used for treatment-emergent anemia or thrombocytopenia, respectively.

Palliative radiotherapy of limited scope (ie, not exposing a significant amount of marrow) for the purpose of symptom relief may be permitted after consultation with the Medical Monitor and will not preclude continuation of TTI-621 administration.

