### **6.8.3 Prohibited Concomitant Treatments**

No other systemic anticancer modalities (including cytotoxic, immunomodulatory, biological, ECP, topical anti-neoplastics or hormonal agents) or additional investigational agents are permitted with the following exceptions in the expansion phase only:

- In subjects with CTCL, chronic use of steroid above a daily equivalent dose of 20 mg prednisone is not permitted on study with the exception of CTCL patients who had been on a stable dose of medium or low-potency topical steroid for 4 weeks before the first dosing of the study drug. These patients can continue to use the same dose of topical steroid for symptom control on study.

Ongoing requirement for systemic corticosteroids of greater than 20 mg prednisone or equivalent is cause for exclusion at screening; the required initiation of corticosteroids during treatment (other than for treatment of an acute symptom) must be discussed with the Medical Monitor and tapered back to 20 mg prednisone or equivalent per day as soon as clinically feasible.

Use of irreversible anticoagulants is not permitted at any time during the study.

Requirement for surgery during treatment will occasion either TTI-621 treatment delay or discontinuation and will be handled case-by-case between the Investigator and Medical Monitor.

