## 7 TESTS AND EVALUATIONS

[figure not shown]
All required observations with their schedules are summarized in [Appendix D, Table 1](#) (Part 2 and 3) and [Appendix D, Table 2](#) (Part 4). Unless otherwise stated, the assessments below pertain to patients enrolled in both Part 3 and Part 4 of the study. Concomitant medications will be recorded from the time of informed consent through the safety follow-up visit. AEs will be recorded from the start of the first dose of study treatment through the safety follow-up visit (see [Section 9.4](#)).

Routine laboratory assessments, such as serum chemistries, hematology, coagulation and urinalysis, will be performed locally. In order to minimize required blood volume, pediatric tubes are suggested (but not required) for hematology and serum chemistries.

Special tests such as PK, ADA, and pharmacodynamic/biomarker samples will be performed centrally or as individually indicated. Additional information on the handling and processing of these samples may be found in the separate Laboratory Manual.

For subjects enrolled in the phase 1b expansion part of the study parts 2-4, there is a window of  $\pm$  2 days (2 days early or 2 days later) for any scheduled treatment days to permit holidays, travel, clinic scheduling and other delays from Week 2 and beyond. If the actual visit occurs greater than 2 days from the planned visit, that planned visit will be considered to have been missed and subjects should proceed with the next planned visit. All response assessments have an allowable window of  $\pm$  1 week. Fresh biopsies, photographs and TCR V $\beta$  whole blood collections also have a  $\pm$  1 week allowable window to align with response assessments.

CCI

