### 7.3 Day 1 Post-TTI-621 infusion (see [Table 7-1](#))

- vital signs at completion of infusion (approximately 60 minutes after Time 0 [ $\pm$  15 minutes]) and 2 and 4 hours after Time 0 [ $\pm$  15 minutes])
- 12-lead ECG within approximately 30 minutes of the completion of infusion (i.e., 60–90 minutes after Time 0)
- Serum for PK:
  - For Part 3: at completion of infusion (approximately 60 minutes after Time 0), 2 hours and 4 hours after Time 0, Day 2 (approximately 24 hours after Time 0). See [Table 7-2](#) and [Appendix D. Table 2](#).
  - For Part 4: at completion of infusion (approximately 60 minutes after Time 0), 2 hours, 4 hours after Time 0, Day 2 (approximately 24 hours after Time 0) and Day 4 (approximately 72 hours after Time 0). See [Table 7-2](#) and [Appendix D. Table 2](#). If a priming regimen is used, see [Appendix F](#) for revised sampling timepoints.
- Hematology:
  - For Part 3: - at completion of infusion (approximately 60 minutes after Time 0), 2 hours, and 4 hours after Time 0 ( $\pm$  15 minutes).
  - For Part 4: at completion of infusion (approximately 60 minutes after Time 0), 2 hours, 4 hours after Time 0 ( $\pm$  15 minutes), Day 2 (approximately 24 hours after Time 0) and Day 4 (approximately 72

hours after Time 0), see [Appendix D. Table 2](#). If a priming dose is used, see [Appendix F](#) for revised sampling timepoints.

- biomarkers ( $\pm$  15 minutes; see Laboratory Manual for details of sample splitting, preparation, and shipping):
  - serum for cytokine/chemokine panel at completion of infusion (approximately 60 minutes after Time 0) and 4 hours after Time 0, (not required for Part 4).
  - whole blood for receptor occupancy at completion of infusion (approximately 60 minutes after Time 0)
- AEs
- concomitant medications

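### The on-study prohibition in Section 6.8.3 names only irreversible anticoagulants and omits the irreversible antiplatelets that exclusion 7 also bars before entry

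*Protocol*

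**What the plan says.** Section 4.2, exclusion 7, applies to both phases and bars two classes before entry: "Use of irreversible antiplatelet/anticoagulant agents within 7 days prior to planned start of treatment (except subjects with thrombocytosis". The exception in that parenthesis is low-dose aspirin given against thrombosis. A closing clause then permits aspirin up to 81 mg/day, with no indication stated, and four reversible anticoagulants (low molecular weight heparin, heparin, warfarin, dabigatran).

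Three statements govern the period on study:

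- Section 6.8.3, prohibition: "Use of irreversible anticoagulants is not permitted at any time during the study".
- Section 6.8.2, general permission: "Other prescribed medications for non-neoplastic conditions are allowed, as well as vitamins and nutritional supplements".
- Section 6.8.2, aspirin: a dose of up to 81 mg/day "is permitted for control of malignant thrombocytosis".

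Section 6.8.2 also permits the same four reversible anticoagulants on study, with dose adjustment for thrombocytopenia and platelets kept above 50 × 10⁹/L or to local standard.

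**The concern.** The entry rule and the on-study rule should cover the same drugs, because the hazard begins with the first infusion. Section 9.5 calls thrombocytopenia an important identified risk and hemorrhage a potential important risk. A patient who stopped an irreversible antiplatelet to satisfy exclusion 7 finds nothing in Section 6.8 that expressly prevents restarting it after the first dose.

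The treatment of related drugs is also uneven. Reversible anticoagulants carry a platelet condition on study. Non-aspirin irreversible antiplatelets carry no on-study rule at all.

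Patient safety is the main thing at stake. A lesser issue is attribution: Grade 3 or higher thrombocytopenia with bleeding is a DLT in Part 4 (Section 3.3.3), and a bleed in a patient on an antiplatelet would be harder to attribute.

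**Working it through.** The point is textual and the plan gives no figure to reproduce. The rules side by side:

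| Drug class | Before entry (exclusion 7) | On study (6.8.2, 6.8.3) |
|---|---|---|
| Irreversible anticoagulants | Barred for 7 days | Barred throughout |
| Irreversible antiplatelets other than aspirin | Barred for 7 days | Not named; general permission for non-neoplastic conditions applies |
| Aspirin up to 81 mg/day | Permitted, no indication stated | Permitted for malignant thrombocytosis |
| Four named reversible anticoagulants | Permitted | Permitted, with platelet condition |

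**Main gap.** The second row is strict before entry and silent afterwards. Every anticoagulant the protocol names is listed as reversible, so 6.8.3 bars a class with no named member and omits the class that exclusion 7 lists first. That looks like a dropped word.

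**Aspirin.** The third row is a mismatch of a different kind. A patient enrolled on 81 mg for a reason other than thrombocytosis satisfies exclusion 7 but falls outside the specific aspirin sentence in 6.8.2.

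**Scheduled post-infusion platelet counts.** These show how much the existing schedule could detect.

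- Part 4, Week 1 (Section 7.3): "at completion of infusion (approximately 60 minutes after Time 0), 2 hours, 4 hours after Time 0", plus Day 2 and Day 4, which makes 5.
- Part 4, Weeks 2 and 3 (Sections 7.4 and 7.5): one each at 4 hours, with Day 2 if clinically indicated. Total 5 + 1 + 1 = 7.
- Part 4 priming regimen (Appendix F): 1 + 5 + 1 = 7 over Weeks 1 to 3.
- Part 4 from Week 4 (Section 7.7 onward; Appendix D, Table 2): 0 scheduled. On-treatment counts are pre-dose, with more at the investigator's discretion.
- Part 3 CTCL and PTCL, Week 1: 3 by Section 7.3 and Appendix D, Table 1. Table 7-1 also shows a 24-hour count that is not marked as Part 4 only, which would make 4.
- Part 3 intensification (Section 7.6): one 4-hour count per step, and (0.5 − 0.2)/0.1 = 3 steps. The total is 6 or 7 if each step is taken once.

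**Context (Sections 1.8.4 and 9.5).** Thrombocytopenia or platelet count decreased was an AE in 47/179 = 26% of subjects. Bleeding events occurred in 24/179 = 13%, Grade 3 in 4/179 = 2%, and none was Grade 4. These figures describe the drug's platelet and bleeding profile. They are not split by antithrombotic use, so they do not measure the effect of the gap.

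**The case against.** The best defence is that 6.8.3 is shorthand for exclusion 7. The specific aspirin permission in 6.8.2 would hardly be needed if antiplatelets were generally allowed, so a continuing restriction was probably intended. This stands against reading the text as a deliberate permission. A reader might infer that the protocol allows irreversible antiplatelets on study by design; the documents support only a failure to prohibit them expressly. If 6.8.3 is shorthand, the same correction is needed.

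A second defence is that patients are well protected, and much of it stands:

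- Each dose requires platelets of at least 75 × 10⁹/L or baseline (Section 6.5.2).
- Grade 3 or higher thrombocytopenia with clinical bleeding requires a delay and then a reduced dose (Table 6-1).
- Once Grade 4 thrombocytopenia is first seen, repeat counts before the next visit are mandatory (footnote to Table 6-1).
- Section 6.7 advises investigators to weigh concomitant medication when managing thrombocytopenia.
- Co-medication is captured: "Concomitant medications will be recorded from the time of informed consent through the safety follow-up visit".
- Exclusion 13 removes "symptomatic coronary artery disease, myocardial infarction within the last 6 months" at entry, which narrows the group likely to need such a drug.

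It would therefore be wrong to infer that a patient on an antiplatelet goes unmonitored. None of these rules says whether the drug may be started, however, and the repeat-count rule works only after a Grade 4 value has been observed.

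Third, Section 9.5 reports no increased risk of bleeding and platelet recovery within 1 week. That limits the weight of the point. A reader might go further and infer that bleeding or DLT results are distorted; nothing in the documents shows that any subject received an irreversible antiplatelet on study.

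Finally, the narrower aspirin rule on study may be deliberate. That cannot be excluded, so the aspirin mismatch is a matter for clarification and not an error.

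**Conclusion.** The gap in wording is real and its severity is minor. Irreversible antiplatelets are barred for 7 days before treatment and not expressly barred afterwards, while the general permission in 6.8.2 covers prescribed drugs for non-neoplastic conditions. The safety relevance rests on the protocol's own statement that most subjects have platelet falls within 24 hours of infusion.

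The size of any effect on bleeding or DLT rates cannot be computed, because the documents give no data on antithrombotic use. That only a few patients would be affected is an assumption. No sample size, error rate or decision rule changes.

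**What to change.** In the 6.8.3 sentence, extend the banned class to irreversible antiplatelet/anticoagulant agents, matching exclusion 7. Keep the present duration; limiting the ban to the treatment period would relax a rule that now covers the whole study. Add an exception for aspirin up to 81 mg/day as permitted in Section 6.8.2. Add that, if a barred agent becomes medically necessary, TTI-621 delay or discontinuation is decided by the route the section already has for surgery: "Requirement for surgery during treatment will occasion either TTI-621 treatment delay or discontinuation and will be handled case-by-case between the Investigator and Medical Monitor".

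In the same amendment, the sponsor should decide whether patients admitted on aspirin up to 81 mg/day for any indication may continue it, and word 6.8.2 accordingly. The two belong together because the new exception refers to 6.8.2. If 6.8.2 stays limited to malignant thrombocytosis, the revised 6.8.3 would bar aspirin for a patient validly enrolled on it for another reason.

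The cost is one amended sentence and one clarification, with no new data or procedures. The downside is that a few patients who need a new irreversible antiplatelet would have TTI-621 delayed or stopped. The current SAP is dated November 2022 and supports an abbreviated study report; if dosing has ended, the change belongs in any successor protocol.

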## 5 ENROLLMENT PROCEDURES

At the time a prospective subject signs the informed consent form, a unique subject number will be assigned and Part 1 of the Registration/Enrollment Form completed and sent to the Sponsor or designee. Subjects will be screened for eligibility according to the criteria outlined in [Section Error! Reference source not found.](#)

### Phase 1b Dose Expansion Phase (Part 2 and 3)

Once a subject is deemed eligible, Part 3 of the Registration/Enrollment Form will be completed and sent to the Sponsor or designee.

### Phase 1b Dose Optimization Phase (Part 4)

Once a subject is deemed eligible, Part 3 of the Registration/Enrollment Form will be completed and sent to the Sponsor or designee, at which time the TTI-621 dose level will be assigned. Additional instructions may be found in the separate Study Manual.

## 6 TREATMENT PROCEDURES

### 6.1 Investigational Product

TTI-621 is formulated as a sterile, clear, preservative-free liquid concentrate in 10 mM sodium phosphate, 150 mM sodium chloride, and water for injection, with pH adjusted to 7.4. Formulated TTI-621 is supplied in single-use vials containing 5.0 mL solution at a concentration of 10 mg/mL. TTI-621 may be stored at -20°C or colder and should be protected from light in a secure storage facility with limited access.

Additional information on the drug product may be found in the Investigator's Brochure; accountability instructions are in the Pharmacy Manual.

### 6.2 Method of Assigning Subjects to Treatment Groups

Subjects in the escalation phase of the study will be sequentially assigned to TTI-621 dose cohorts at the time of enrollment as described in [Section 3.2.1](#). For the expansion phase of the study, subjects will receive treatment based on the dose selected from the escalation phase, unless otherwise specified (see [Section 3.3](#)).

## 6.3 Treatments Administered (All Phases)

### 6.3.1 Dosing Instructions

#### *General*

Premedication with an antihistamine and acetaminophen is required for all subjects prior to infusion of TTI-621.

TTI-621 will be thawed at room temperature and the required dose diluted into 250 mL of 0.9% sodium chloride for injection USP as further described in the Pharmacy Manual. If not used immediately, the prepared infusate may be stored as described in the Pharmacy Manual. The assigned dose of TTI-621 will be administered IV over 60 minutes (see [Section 6.4.1](#) for expansion phase instructions). The start of the infusion (Time 0) is defined as after priming, immediately before commencement of the infusion. End of infusion is defined as the time immediately after the flush.

Vital signs will be monitored as outlined in [Section 7](#).

The individual dose is determined based on the subject's current body weight. Body weight can be rounded per institutional procedures when calculating doses. Body weight will be taken weekly through Week 8, then every other week (Weeks 10, 12, etc.) After Week 8, the weight taken at the prior visit may be used to calculate dose (e.g. weight at Week 8 used for Week 9 dosing).

Each subject will receive TTI-621 in accordance with the assigned dose until disease progression, unacceptable toxicity, or other reasons for treatment discontinuation occur. For patients who have been given weekly infusion of TTI-621 for more than a year and are receiving clinical benefit (objective response or clinically meaningful long-term stable disease), investigators may exercise their discretion to reduce the dosing frequency from weekly to bi-weekly following the discussion and approval from the sponsor or designees. In the context of treatment discontinuation, unacceptable toxicity will include any Grade 4 TTI-621-related nonhematologic toxicity or a TTI-621-related toxicity that requires a dose delay of more than 3 weeks.

In the absence of disease progression, subsequent TTI-621 doses may be delivered based upon subject's clinical status with dose modifications per [Section 6.5](#).

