### 6.5.1 General Principles

Patients will be evaluated according to the Schedule of Assessments (See [Appendix D. Table 1](#) and [Appendix D. Table 2](#)) for possible toxicities that may have occurred after the previous dose(s). Toxicities are to be assessed according to the NCI CTCAE version 4.03. All toxicities that occur during the study will be actively managed following the standard of care per local institutional practice unless otherwise specified in the protocol. The investigator should try to the best of his/her ability to assess whether an AE is related or possibly related to study drug, and dosing actions of TTI-621 will then be considered accordingly.

In general, patients who have the TTI-621 dose held due to treatment-related or possibly related AE may resume study drug after resolution of the AE, at the same dose level or at a reduced level (dose reduction) by at least 1 dose level. When a dose reduction occurs, the TTI-621 dose will be reduced to the next lower dose either by following the ramp-up dosing regimen in Part 3 or on the established safe dose during phase 1b dose optimization part 4. If the initial dose adjustment does not provide sufficient relief, the dose of TTI-621 can be further reduced if the investigator considers that the patient is benefiting from study treatment and may benefit at a further dose reduced dose level of TTI-621. When a dose reduction of TTI-621 is required due to toxicity, no dose re-escalation will be permitted. If TTI-621 dosing is delayed for > 21 days for TTI-621-related or possibly related toxicities despite supportive treatment per standard clinical practice or more than 2 dose reductions are required in a patient, the investigator should consider discontinuing the patient from study treatment, unless the investigator, after risk-benefit assessment, considers that the patient may benefit from continued study treatment after resolution of AEs and when the re-treatment criteria are satisfied per [Section 6.5.2](#). The patient will continue to be followed for 30 days after the last administration of TTI-621.

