### **6.5.3 Dose Modification Guidelines for TTI-621-related toxicities**

Please refer to Table 6-1 for dose delay and reduction recommendations for hematologic and non-hematologic toxicities. When the dose of TTI-621 is withheld based on the following criteria outlined below, clinical and laboratory re-evaluation should be repeated at least weekly or more frequently at investigator discretion following standard of care practice until the toxicity resolves to  $\leq$  Grade 1 or baseline or to a level assessed to be acceptable per [Section 6.5.1](#) and [Section 6.5.2](#) and/or by the investigator upon agreement from the medical monitor. Upon recovery, TTI-621 may be reinitiated either at the same dose level or at a reduced dose level. In events where there are transient lab value abnormalities that, based on investigator assessment, are not clinically significant or related to disease and not the study drug, continuation of therapy without following the dose modification guideline is permissible upon discussion with the sponsor medical monitor.

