
Grade 3 or greater non-hematologic toxicity related to TTI-621 with the following exceptions:
 
 
• Grade 3 nausea and/or vomiting lasting <72 hours with standard supportive care
 
• Transient Grade 3 fatigue lasting <math>\leq</math>72 hours
 
• Transient asymptomatic Grade 3 laboratory abnormalities that last <72 hours with standard supportive care and considered not clinically significant following agreement between investigators and the sponsor or designees.
 
	
For Grade 3 events, delay TTI-621 dosing until the re-treatment criteria is met, then resume TTI-621 at a reduced dose by 1 dose level.
 
No dose reduction is required for the exceptions listed.
 
For Grade 4 events, discontinuation of TTI-621 should be considered. If, per investigator's assessment, it is in the patient's best interest to continue the treatment, TTI-621 treatment can be resumed when the AE resolves to a level that meets the re-treatment criteria
 
Do not intensify dose (Part 3)

Grade 3 or greater non-hematologic toxicity NOT related to TTI-621	Investigator's discretion to withhold or decrease dose of TTI-621. Do not intensify dose of TTI-621 until the resolution of the AEs to Grade 1, baseline, or a level (must be $\leq$ Grade 2) determined to be acceptable per investigator assessment (Part 3)

Grade 3 anemia	
Delay TTI-621 dosing until resolution to <math>\leq</math> Grade 1 or baseline, then resume TTI-621 treatment:
 
 
• at the same dose if dose delay for 1 week;
 
• at a reduced dose by 1 dose level if dose delay for <math>> 1</math> week;
 
• at a reduced dose by 1 dose level if the event recurs
 
• Dose intensification can occur only when there is no occurrence of the same event upon re-dosing of TTI-621 at the same dose for two consecutive weeks. When dose reduction occurs, no further dose intensification will be allowed (Part 3).
 

Grade 4 anemia	
Discontinuation of TTI-622 should be considered. If it is in the patient's best interest to continue TTI-622 per investigator assessment, withhold dose until resolved to <math>\leq</math> Grade 1 or baseline, then reduce by 1 dose level.

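### Table 6-1 names no dose reduction on resuming after a late related Grade 4 non-hematologic event, although a Grade 3 event in the same cell requires one

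*Protocol*

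**What the plan says.** Section 6.3.1 of the protocol stands under a heading for all phases. It continues treatment until progression, unacceptable toxicity or another reason to stop, and defines the second of these: "unacceptable toxicity will include any Grade 4 TTI-621-related nonhematologic toxicity or a TTI-621-related toxicity that requires a dose delay of more than 3 weeks". Its next paragraph refers later doses to Section 6.5. Section 6.9 again lists related Grade 4 non-hematologic toxicity as unacceptable, but permits withdrawal rather than requiring it.

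Section 6.5 is stated to apply to the whole Phase 1b expansion (Parts 2, 3 and 4). In its Table 6-1, one cell covers related non-hematologic toxicity of Grade 3 or higher:

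- Grade 3, three listed exceptions apart: hold dosing "until the re-treatment criteria is met, then resume TTI-621 at a reduced dose by 1 dose level".
- Grade 4: "For Grade 4 events, discontinuation of TTI-621 should be considered". If the investigator judges continuing to be best for the patient, "TTI-621 treatment can be resumed when the AE resolves to a level that meets the re-treatment criteria". No dose is stated.
- The cell also bars further intensification in Part 3.

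The Grade 4 anemia row has the same structure, but after recovery to "Grade 1 or baseline, then reduce by 1 dose level".

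The general rules permit either dose. Under Section 6.5.1 a patient whose dose was held "may resume study drug after resolution of the AE, at the same dose level or at a reduced level". Under Section 6.5.3, on recovery, "TTI-621 may be reinitiated either at the same dose level or at a reduced dose level".

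**The concern.** Within one table cell the graver event carries the weaker rule on dose. A patient who recovers from a related Grade 4 non-hematologic event may be given the dose that preceded it, while a patient who recovers from a Grade 3 event must step down. The anemia row shows that the authors knew how to name a cut for a Grade 4 event when resumption is allowed, so the silence here looks like an omission.

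The second difficulty is which section controls. Section 6.3.1 classes the event as one that ends treatment; Table 6-1 allows treatment to go on. Without an express order of precedence, one site could stop and another resume after the same event, each citing the protocol. At stake is the safety of re-dosing, and consistency between sites in a multicenter study.

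**Working it through.** The documents give no figure to reproduce. The check compares the rules, then sizes the dose difference and the likely frequency.

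**1. Resumption rules side by side**

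| Related toxicity | Source | Dose on resumption |
|---|---|---|
| Grade 3 non-hematologic, not an exception | Table 6-1 | one level lower, required |
| Grade 4 non-hematologic | Table 6-1 | none named |
| Grade 4 anemia | Table 6-1 | one level lower, required |
| Grade 4 infusion reaction | Table 6-1, 6.7 | no resumption |
| DLT in the DLT period, or DLT-like toxicity in the first 21 days | 6.5.1 | at least one level lower, if resumed at all |
| Not resolved by three weeks | 6.5.2 | at least one level lower, if resumed at all |
| General rule | 6.5.1, 6.5.3 | same or lower |

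(The anemia row prints the product as TTI-622; I read this as TTI-621.)

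**2. What is left uncovered.** Removing the rows that already protect the patient leaves a related Grade 4 non-hematologic event, not an infusion reaction, that starts after the DLT window and resolves within three weeks. The window ends at Day 21, or up to Day 28 in Part 4 if a held dose extends it (Section 3.3.2). For this event only the general rule applies, and it allows the same dose. Medical monitor input becomes mandatory under 6.5.2 only if recovery stops short of Grade 1, baseline or a listed exception.

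**3. Where the higher doses fall.** With Week w Day 1 = Day 1 + 7(w − 1), the fastest Part 3 ramp-up under Section 6.5.4 is:

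- Days 1 and 8: 0.2 mg/kg
- Day 15: 0.3 mg/kg
- Day 22: 0.4 mg/kg
- Day 29: 0.5 mg/kg

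Section 7 allows ±2 days from Week 2, so the first 0.4 mg/kg dose may be given from Day 20 (22 − 2) and the first 0.5 mg/kg dose from Day 27 (29 − 2). Dosing at these levels therefore falls mostly, but not wholly, after Day 21. In Part 4 weekly dosing continues after the window at the assigned level, planned up to 1.4 mg/kg.

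**4. Size of the cut that Grade 3 requires and Grade 4 does not.** Cut = (current − next lower) / current.

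- Part 3: (0.5 − 0.4)/0.5 = 20.0%; (0.4 − 0.3)/0.4 = 25.0%
- Part 4: (0.7 − 0.5)/0.7 = 28.6%; (1.0 − 0.7)/1.0 = 30.0%; (1.4 − 1.0)/1.4 = 28.6%

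The Part 4 figures assume that the next lower planned level is the dose reduced to; Section 6.5.1 speaks of an established safe dose instead.

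**5. Frequency.** The documents do not count in-scope events. The nearest data are these:

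- Section 9.5 reports Grade 3–4 ALT/AST elevation in 3 of 179 subjects, none as an SAE. Section 1.7 describes one Grade 3 case in Phase 1a, which is outside Section 6.5. If that subject is one of the three and did not worsen, at most 3 − 1 = 2 of the 161 expansion subjects had Grade 4: 2/161 = 1.24% (exact 95% CI 0.15% to 4.42%). The lower end is 0/161 (0% to 2.27%). Relatedness is not stated.
- By Section 1.7, apart from infusion reactions, no single non-hematologic term had related Grade 3 or higher events in more than 2 of 179 subjects (1.12%). This limits each term, not the sum over terms.

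**The case against.** The best defense starts from precedence. Section 6.3.1 itself hands later doses to Section 6.5, Section 6.5 declares that it covers the Phase 1b expansion, and Section 6.9 only permits withdrawal. On that reading there is no conflict. On the opposite reading treatment ends, and there is no same-dose gap. This stands: the two problems rest on alternative readings and should not be added together. Whichever reading is meant, one of the two texts needs changing.

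Second, Grade 4 is handled more strictly at the first step. Discontinuation must be considered, and resumption needs a positive judgment for the individual patient; Grade 3 requires neither. The cell also says that the listed Grade 3 exceptions need no reduction, which could be taken to imply a reduction for everything else in the row. These points soften the contrast. But an implied cut is a weak basis for a dosing rule when two general provisions expressly allow the same dose.

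Third, there are safeguards outside the cell. Life-threatening events are SAEs, reported within 24 hours (Section 9.3). The sponsor may withdraw the subject (6.9), and the SRC can discuss individual cases (3.4). The investigator and medical monitor may agree another modification (6.5.1). All of this stands, though not every Grade 4 laboratory event is an SAE, and none of these provisions requires a lower dose.

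Finally, requiring medical monitor agreement would go beyond the anemia row, which leaves resumption to the investigator. That is correct, so it is not part of the core fix.

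**Conclusion.** The concern holds in a narrow form. For a related Grade 4 non-hematologic event other than an infusion reaction, starting after the DLT window and resolving within three weeks, Table 6-1 allows resumption with no reduction named. Its own Grade 3 and Grade 4 anemia rules require one level. The dose difference is 20% to 25% at the upper Part 3 doses and 28.6% to 30% between planned Part 4 levels, on the next-level assumption. The bar on intensification in Part 3 stops a rise but does not lower the dose.

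A reader might infer more than the documents support:

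- That full-dose resumption is instructed. It is permitted, not directed.
- That the protocol plainly contradicts its own stopping rule. The context favors Section 6.5; what is missing is an express statement.
- That every 0.4 and 0.5 mg/kg dose in Part 3 lies beyond the protected window. The visit window allows a 0.4 mg/kg dose on Day 20 or 21.
- That patients have been re-dosed after such events. No related Grade 4 event in scope is documented, and the frequency is probably small.
- That dose finding is compromised. Section 6.6 counts a DLT toward the MTD whatever happens on resumption.

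This is a worthwhile safety wording correction. It does not challenge the design or the analysis.

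**What to change.** 1. In the Grade 4 part of the Table 6-1 non-hematologic cell, add that TTI-621, if resumed, is resumed at a dose reduced by at least one level. Medical monitor agreement may be added as an option.
2. Amend Section 6.3.1 so that its definition of unacceptable toxicity defers expressly to Section 6.5 for Parts 2 to 4. If mandatory discontinuation is what the sponsor intends, change Table 6-1 and Sections 6.5.1 and 6.5.2 to match 6.3.1 instead.

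Under the first option of step 2, the cost is a wording change to one table cell and one sentence, and slightly less investigator discretion over the resumption dose. Sample size, DLT criteria and MTD rules are unchanged. The SAP is written for an abbreviated study report; if dosing has already ended, which the documents do not state, the change would help only later protocols that reuse this table.
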